13.8 Analysis of Exploratory Endpoints

13.8.1 Characterizing T cell populations

The analyses of pre- and post-treatment PB and BM specimens for immune parameters will be descriptive and graphical in nature. Data will be summarized for each patient group separately (blinatumomab plus nivolumab; blinatumomab plus nivolumab and ipilimumab). Flow values at each time point will be summarized using geometric means and standard deviation. Differences in baseline values between patient subgroups will be explored using linear regression models. We are specifically interested in determining what pretreatment signature is associated with outcome, such as having a complete response or becoming refractory. To this end, we will use logistic regression models with ROC analysis to describe which pretreatment parameters are potential predictors of outcomes following treatment. Values will be checked for skewness and log-transformed as appropriate. The change in flow values at each time point after blinatumomab and blinatumomab plus checkpoint inhibitor(s) relative to the baseline value will be modeled using mixed-effects, linear regression models that include fixed effects for time point and a random effect for the patient to account for within-patient correlation of measurements. Post-treatment changes in T cell populations will be correlated with clinical outcomes such as CR vs. No CR or MRD vs. No MRD using interaction tests. T cell subsets in the PB and BM defined by multicolor flow cytometry will be summarized before and after treatment with blinatumomab alone or plus checkpoint inhibitors by treatment group using summary statistics. Differences in T cells before and after treatment will be explored using non-parametric Wilcoxon signed rank tests or paired t tests as appropriate. The expression of co-inhibitory/-stimulatory molecules will also be examined in the same way.

13.8.2 Characterization of T cell transcriptional signature before and after treatment.

Expression levels will be summarized at pre-treatment and post-treatment using standard descriptive statistics. Differentially-expressed genes and corresponding fold-changes will be analyzed using standard statistics and through the use of Ingenuity pathway analysis as described previously. We will identify differentially-expressed genes by patient subgroups such as CR v. NR and MRD v. No MRD using interaction tests.

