2.2.1.2.4 Pharmacodynamics/Biomarkers²⁴

Pharmacodynamic (PD) measures included lymphocyte subsets and cytokines. The response to blinatumomab was characterized by peripheral B-cell depletion, T-cell activation and redistribution as well as transient cytokine elevation. Consistent PD profiles were observed across clinical trials following the cIV regimen.

T-cell dynamics: Following blinatumomab cIV infusion, peripheral T-cell counts initially declined within 1 to 2 days to very low levels, a phenomenon described as redistribution from periphery to tissues. After the initial decline, T-cells started to increase and reached baseline levels in about 14 days. Increase of T-cell counts above baseline was found in some subjects. There was no difference between the dynamics of CD4⁺ and CD8⁺ T cells. A high inter-individual variability was observed in T-cell baseline levels. The time to return to baseline was variable across subjects (10 to 30 days).

B-cell Dynamics: B-cell counts in peripheral blood decreased rapidly and became undetectable during treatment at doses $\geq 5 \mu\text{g}/\text{m}^2/\text{day}$ (or $9 \mu\text{g}/\text{day}$) in most subjects. No recovery of B-cell counts was observed during the drug-free period between treatment cycles. Incomplete depletion of B cells was observed at doses of 0.5 and $1.5 \mu\text{g}/\text{m}^2/\text{day}$. High inter-individual variability was found in baseline B-cell counts. Associated with the B-cell depletion, decreases in immunoglobulin (Ig) levels have been observed. Long-term Ig levels were measured in 6 MRD-positive ALL subjects treated with blinatumomab. Partial to complete recovery of IgM and IgG levels and incomplete recovery of IgA were observed during the long-term safety follow-up period.³⁴

Cytokine Dynamics: The measured cytokines were TNF- α , IL-2, IL-6, IL-8, IL-10, IL-12, IL-4, and IFN- γ . Transient elevation of cytokines was observed in some subjects in the first 2 days following the blinatumomab infusion. The elevated cytokine levels returned to baseline within 24 to 48 hours during the infusion period. In subsequent treatment cycles, cytokine elevation was only observed in few subjects with much less intensity. The magnitude of cytokine elevation

trended higher at higher doses. The inter-subject variability in cytokine elevation was large.

See Section 8.1.1 for drug information.

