2.3.3 Improving Outcomes in ALL after Blinatumomab Treatment

Though the initial study of blinatumomab in relapsed/refractory Pre-B ALL demonstrated a CR rate of 69%, a subsequent larger study in patients at high risk for poor outcomes led to a more modest response rate of 43%.^{31,32} This response rate was comparable to that seen with cytotoxic chemotherapy in prior studies in relapsed Pre-B ALL.⁴ Furthermore, this study also showed the limited durability of responses to blinatumomab with a median RFS of just 6.9 months among those who achieved MRD negative status following treatment. Thus while blinatumomab has shown significant activity with an acceptable safety profile in patients with relapsed or refractory Pre-B ALL, many patients still fail to achieve a response or relapse shortly after achieving a response, including MRD responders. Given the short duration of remission and high risk of relapse following blinatumomab, consolidation with an allogeneic HSCT has been shown to be a feasible strategy; however, only a subset of patients who achieve remission with blinatumomab will be candidates for allogeneic HSCT and post-transplant relapse remains a problem.^{32,81} Thus, there is a need to develop additional strategies to increase and prolong responses after blinatumomab treatment. Monitoring of T-cell kinetics in relapsed and refractory patients treated on the initial phase II study identified that the expansion of CD3⁺ T cells during the first 2 cycles correlates with the response, with long-term survivors having a higher degree of T-cell and T_{EM}-cell expansion. Interestingly, T-cell expansion was limited in MRD responders with shorter survival and was not seen in MRD non-responders. B cell kinetics revealed their rapid and persistent clearance in MRD responders while detectable return of peripheral B cells was noted before cycle 2 in non-responders.⁸¹ Given the correlation between T-cell expansion, MRD clearance and subsequent long-term survival after blinatumomab treatment, augmenting the initial or early anti-leukemia T-cell response following blinatumomab is a rational strategy to improve response rate and extend its durability.

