9.2.1 Flow cytometry studies

- 9.2.1.1 **Exploratory/Ancillary Correlative Studies #1: T-cell subsets distribution (CD4⁺, CD8⁺, T_{regs}, T_{effs}), their differentiation status and expression of co-signaling molecules and canonic transcription factors, NK cells, and B cells before and post-blinatumomab, and immune checkpoint inhibitor(s) therapy in both peripheral blood and the bone marrow microenvironment (Serial PB and BM samples collected at all time points as indicated in Section 9.1). We will perform multi-parameter flow cytometry on PB and BM specimens obtained at designated**

time points indicated in the Section 9.1 and on the Study Calendar to examine the effect of blinatumomab and checkpoint inhibition on T, NK and B cell dynamics in two different compartments in ALL patients. The analysis will be performed using three pre-determined panels of mAbs including but not limited to those specific for CD3, CD4, CD8, PD-1, CD45RA, CCR7, CD25, CD27, CD28, CD57, CD69, Ki-67, T-bet, CD95, CD127, FoxP3, HLA-DR, CTLA-4, TNFR11, TIM-3, LAG-3, CD160, 2B4, BTLA, KLRG-1, Eomes, Blimp-1, CD16, and CD56. This multi-parametric flow cytometry approach allows examination of different CD4⁺ and CD8⁺ T-cell subpopulations (expressing CD45RA, CCR7, CD27, CD28 and CD57), their expression of co-signaling molecules, proliferation (% Ki-67 positive cells) and activation status (CD69, HLA-DR and TNFR11) as well as phenotypic separation of human CD4⁺FoxP3⁺ T cells into three distinct subpopulations. Natural killer cells (NK), NK-T cells will be enumerated using CD16 and CD56 (NK/NK-T cells). Additionally kinetics and durability of B cell depletion (CD19) will be assessed. [name] (co-investigator) and his lab have extensive experience in characterizing different T cell subpopulations in leukemia patients at diagnosis, during and after chemotherapy, after allogeneic HSCT, and in follow up as published.⁷⁴ Our studies in AML clearly show differences in T cell distribution, activation status, and expression of different co-signaling molecules between the PB and BM and depending the disease status and response to therapy.⁷⁴

NOTE: See BIOASSAY TEMPLATE IN Appendix C.

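### Section 13.8.1 summarises flow values by geometric mean, which gives zero, no value or noise for peripheral B cells once they are undetectable on treatment

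*Combined protocol and SAP*

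**What the plan says.** The summary rule in Section 13.8.1 is definite: "Flow values at each time point will be summarized using geometric means and standard deviation". Appendix C, item 6, repeats it. The only related instruction is "Values will be checked for skewness and log-transformed as appropriate". Neither place gives a detection limit, a substitution value or a rule for zeros.

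The heading of Section 13.8.1 names T cells, but its opening sentence covers immune parameters in blood and marrow generally. B cells are part of that set: Sections 1.3.1 and 13.3.3.1 list them beside T-cell subsets and NK cells, and Section 9.2.1.1 adds "Additionally kinetics and durability of B cell depletion (CD19) will be assessed". Sections 13.8.2 to 13.8.5 cover the T-cell transcriptional signature, blasts, cytokines and the T-cell repertoire, so no other analysis rule applies to B cells.

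On what to expect, Section 2.2.1.2.4 reports that "B-cell counts in peripheral blood decreased rapidly and became undetectable during treatment" at 9 µg/day or above in most subjects, and that "No recovery of B-cell counts was observed during the drug-free period between treatment cycles". Section 2.3.3 reports that "B cell kinetics revealed their rapid and persistent clearance in MRD responders while detectable return of peripheral B cells was noted before cycle 2" in non-responders.

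**The concern.** A geometric mean is defined usefully only for positive values. The protocol's own background section predicts that, for one of the listed flow measurements, most patients will have nothing to measure for much of the treatment period. The planned statistic therefore fails where the exploratory question lies, namely how fast and for how long B cells are cleared.

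The undetectable values also carry information. By Section 2.3.3, cleared B cells go with MRD response and returning B cells with non-response. If an analyst met the zeros without a written rule and left them out, the on-treatment summary would come mainly from patients whose B cells had returned, and depletion would look weaker than it was. If the zeros were replaced by a small constant, that constant would largely set the result.

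**Working it through.** The plan gives no figure for this analysis, so there is none to reproduce. The check has three steps.

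**1. Are undetectable values expected at the sampled time points?** Every dose level in the Section 5.2.1 schedule gives 9 µg/day on days 1 to 7 and 28 µg/day on days 8 to 28 of cycle 1. Section 9.1 samples blood around days 8 to 11, on days 15 and 22, on days 29 to 35, before cycle 2, and at the end of cycle 2. Several time points therefore fall within the period that Section 2.2.1.2.4 describes as depleted.

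**2. What does one zero do?** The geometric mean is (x₁ × x₂ × … × xₙ)^(1/n) = exp(mean of log x). Take six assumed values of 2, 1, 0.5, 0.3, 0.2 and 0 percent. The product is 0, so the geometric mean is 0. By the log route, the mean log is minus infinity and the SD of the logs is undefined. With 0.1 in place of the 0, the geometric mean is 0.43.

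Assume that patients are independent, that each has probability q of being undetectable, and that undetectable is recorded as zero. The chance of at least one zero among n patients is then 1 − (1 − q)ⁿ. Section 13.5 gives 12 patients for the combination arm; 6 is the size of one expansion cohort. The protocol does not state q.

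| Assumed q | n = 6 | n = 12 |
|---|---|---|
| 10% | 1 − 0.90⁶ = 46.9% | 1 − 0.90¹² = 71.8% |
| 25% | 1 − 0.75⁶ = 82.2% | 1 − 0.75¹² = 96.8% |
| 50% | 1 − 0.50⁶ = 98.4% | 1 − 0.50¹² = 99.98% |

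Since most means more than half, the last row is a floor if the background statement carries over to this trial.

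**3. How much does the unstated handling matter?** Illustrative data, not from the documents: 12 patients, five with 2, 1, 0.5, 0.3 and 0.2 percent, and seven undetectable. The product of the five positive values is 0.06.

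- Zeros kept: geometric mean 0.
- Zeros dropped: 0.06^(1/5) = 0.57%.
- Zeros replaced by c: (0.06 × c⁷)^(1/12), which is 0.054% for c = 0.01%, 0.036% for c = 0.005% and 0.014% for c = 0.001%.
- Direct description: 7 of 12 undetectable, median 0, range 0 to 2%.

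Across dropping and substitution the summary moves from 0.57% to 0.014%, about 40-fold (0.57 / 0.014 ≈ 41), on identical data. The values of c are arbitrary, because the documents set no detection limit for B cells.

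**The case against.** Several points on the other side stand.

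- **Scope.** A reader might infer that every flow analysis is affected. The documents do not support that. Most T-cell subsets can be expected to have positive values. Section 13.8.3 gives blasts their own plan with no geometric mean, and what it analyses is expression on blasts: with no blasts, the value is missing rather than zero.
- **Appendix C.** Its template is for T-cell markers, and its antibody table has no CD19. The repeated sentence there matters for rare T-cell subsets, not for B cells. Its minimum of 10,000 events does not name the parent gate, so a B-cell detection limit cannot be derived from it.
- **Models.** A reader might infer that the mixed models in Section 13.8.1 also fail. Log transformation there is conditional, and a model of untransformed change accepts zeros. The explicit log-scale model in Appendix C, item 5, describes the laboratory's past work.
- **Dropping zeros.** Nothing in the documents says this will happen. The loss of the contrast between responders and non-responders is a risk left open by silence, not a planned step. Individual plots, which the descriptive and graphical approach allows, would still show depletion.
- **Spread.** The standard deviation may be meant as the geometric SD. The wording is ambiguous rather than wrong.
- **Zeros kept.** In the illustration the median is also 0, so the gain comes mainly from reporting how many patients are undetectable.

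Undetectable also need not be recorded as exactly zero. Gating background could leave small positive readings. That does not rescue the statistic: the geometric mean is then finite but driven by noise near the detection limit.

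**Conclusion.** The point holds in a limited form. For peripheral B cells, the summary named in Section 13.8.1 is very likely to be zero, undefined or dominated by near-limit noise at on-treatment time points, and the plan does not say what to report instead. With 12 patients, at least one zero has probability 72%, 97% or over 99.9% for assumed undetectable shares of 10%, 25% or 50%.

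This rests on three assumptions: the background findings from other blinatumomab studies apply here, undetectable values are recorded as zero or close to it, and patients are independent. Those findings concern peripheral blood, so the expectation does not extend to marrow. The same gap touches any rare T-cell subset with no events.

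A reader might go further and infer bias in the trial's conclusions. The documents do not support that: these are exploratory, descriptive summaries, and the DLT, MTD, response, duration-of-response and survival analyses do not use them. It is a modest correction, best made before the flow data are examined.

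**What to change.** In Section 13.8.1:

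1. State the detection limit for each flow marker, set by the laboratory for the gate used.
2. For B cells, and any other flow marker with values below that limit, report at each time point the number and percent below it, with median and range.
3. Describe B-cell depletion over time as detectable versus undetectable, by response.
4. Keep the geometric mean only where all values are positive, and say that its spread is the geometric SD or a back-transformed 95% confidence interval.

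Appendix C, item 6, needs only the same zero-handling wording for rare T-cell subsets. A left-censored mixed model need not be required: with about 12 patients, most of them censored, it would be poorly identified.

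The cost is a wording change, slightly more analysis work and a less compact summary table. No new samples or data are needed.

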When the safety of blinatumomab in combination with nivolumab is confirmed, the study will expand to treat patients with this combination plus ipilimumab. A standard 3+3 design will be used to assess the safety and tolerability of the combination. Two dose levels (DL B1, DL B-1,) are available. If DL A1 was deemed safe, then three patients will be enrolled at DL B1. If ≤ 1 of 3 patients experience a DLT during the first cycle of treatment (42 days), at DL B1, an additional 3 patients will be enrolled at DL B1. If no more than 1 of 6 patients experience a DLT, then it will be defined as the MTD. If 2 or more of 3 or 6 patients experience a DLT at DL B1, then dose de-escalation may be implemented BUT ONLY after CTEP approval and the next three patients may be enrolled at DL B-1. If ≤ 1 of 3 patients experience a DLT during the first cycle of treatment (42 days), an additional three patients will be enrolled at DL B-1. If 2 or more of 3 or 6 patients experience a DLT at DL B-1, then dose escalation will be halted and the combination of blinatumomab, nivolumab and ipilimumab will not be further pursued in this patient population unless additional data become available supporting different doses or schedules of nivolumab and ipilimumab administration. This will require review of all toxicity, discussion with CTEP and official study amendment.

When the MTD of blinatumomab in combination with ipilimumab and nivolumab is determined, an additional 6 patients will be enrolled in an expansion cohort to further characterize safety, tolerability and any preliminary signs of biological or clinical activity of the triplet blinatumomab/nivolumab plus ipilimumab. An expansion cohort of 6 subjects will be also pursued at MTD for doublet of blinatumomab and nivolumab only to further characterize safety, tolerability and any preliminary signs of biological or clinical activity in this cohort.

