13.5 Sample Size/Accrual Rate

In the dose escalation phase of this study, the sample size is determined by the number of DLTs observed. The minimum sample size for this first part of the study will be 6 patients at DL1 and DL-1 (if necessary), and a maximum sample size of 12 patients. During the dose escalation phase of the combination arm, the minimum number of patients treated will be 3 and maximum will be 6 at each dose level. If the combination is deemed safe and the expansion cohort is enrolled, the sample size will be either 9 or 12 at that dose level. The maximum total sample for the entire study will be 36 patients.

The anticipated complete response (CR) rate in this patient population is approximately 40%. With a minimum sample size of 12 subjects in the combination arm, the probabilities of observing at least 5 responses out of 12 patients (41.7% CR rate) would be 0.42, 0.56, and 0.70 if the true CR rate is 35%, 40%, and 45%, respectively. If the true CR rate is less than 15%, the chance of observing 5 responses out of 12 would be 0.024 or less. This sample size also allows for estimation of the CR rate with precision (half the width of the 95% exact binomial confidence interval) being no wider than 25.5%.

PLANNED ENROLLMENT REPORT

Racial Categories	Ethnic Categories				Total
	Not Hispanic or Latino		Hispanic or Latino		
	Female	Male	Female	Male	
American Indian/ Alaska Native	0	0	0	0	0
Asian	1	0	0	0	1
Native Hawaiian or Other Pacific Islander	0	0	0	0	0
Black or African American	1	2	0	0	3
White	7	13	3	3	26
More Than One Race	0	0	0	0	0
Total	9	15	3	3	30

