6. Clinical utility of the integrated assay: Flow values at each time point will be summarized using geometric means and standard deviation. Differences in baseline values between patient subgroups will be explored using linear regression models. We are specifically interested in determining what pretreatment signature is associated with outcome, such as having a complete response or becoming refractory. To this end, we will use logistic regression models with ROC analysis to describe which pretreatment parameters are potential predictors of outcomes following treatment. Values will be checked for skewness and log-transformed as appropriate. The change in flow values at each time point after blinatumomab and blinatumomab plus checkpoint inhibitor(s) relative to the baseline value will be modeled using mixed-effects, linear regression models that include fixed effects for time point and a random effect for the patient to account for within-patient correlation of measurements. Post-treatment changes in T cell populations will be correlated with clinical outcomes such as CR vs. No CR or MRD vs. No MRD using interaction tests. T cell subsets in the PB and BM defined by multicolor flow cytometry will be summarized before and after treatment with blinatumomab alone or plus checkpoint inhibitors by treatment group using summary statistics. Differences in T cells before and after treatment will be explored using non-parametric Wilcoxon signed rank tests or paired t tests as appropriate. The expression of co-inhibitory/-stimulatory molecules will also be examined in the same way.

References:

[figure not shown]

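### The marker screen in 13.8.1 and Appendix C item 6 reports apparent AUCs over at least 29 markers with no reference for how high the best AUC goes by chance (minor; cheap to improve)

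*Combined protocol and SAP*

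**What the plan says.** Section 13.8.1 states the aim: "We are specifically interested in determining what pretreatment signature is associated with outcome, such as having a complete response or becoming refractory". The method follows: "we will use logistic regression models with ROC analysis to describe which pretreatment parameters are potential predictors of outcomes following treatment". Appendix C item 6 carries the same aim and method ("We are specifically interested in determining what pretreatment signature is associated with outcome").

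The input list is in Section 9.2.1.1: "three pre-determined panels of mAbs including but not limited to those specific for CD3, CD4, CD8, PD-1", and so on. I count 29 named antigens, in blood and in marrow.

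On the analysis set, 13.8.1 says "Data will be summarized for each patient group separately", naming the doublet and the triplet. The logistic/ROC sentence does not mention regimen. Section 13.5 works "With a minimum sample size of 12 subjects in the combination arm", and Section 13.4 adds to each regimen's six escalation patients: "an additional 6 patients will be enrolled in an expansion cohort".

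The plan is modest about status. It says "The analyses of pre- and post-treatment PB and BM specimens for immune parameters will be descriptive and graphical in nature", calls the predictors potential, and labels the assay exploratory in Appendix C. Section 9.2 nevertheless gives, as one goal, finding candidate biomarkers to help choose which ALL patients should get checkpoint inhibitors with blinatumomab in future.

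I found no marker shortlist, AUC threshold, multiplicity statement, cross-validation, optimism correction or limit on model size in either 13.8.1 or Appendix C item 6.

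**The concern.** An AUC computed in the same few patients used to pick the marker is optimistic, and more so when it is the best of many. A reader shown a best AUC of, say, 0.86 needs to know what the best AUC would have been had no marker mattered. The plan supplies no such reference. Without it, the markers carried into later work may be a ranking of noise. The stake is which hypotheses get pursued and possibly used to select patients in later trials; no decision within this trial depends on it.

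**Working it through.** **The plan's own figure.** Section 13.5 gives the probability of at least 5 remissions in 12 patients as 0.42, 0.56 and 0.70 at true rates of 35%, 40% and 45%, and at most 0.024 below 15%. The exact binomial tail gives 0.417, 0.562, 0.696 and 0.0239 (at 15%), so these reproduce. The plan offers no corresponding calculation for the marker analysis.

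**Inputs.**
- Markers: 29 (Section 9.2.1.1); 2 × 29 = 58 values with both compartments.
- Patients: 6 escalation + 6 expansion = 12 per regimen; 24 if both are pooled.
- Remissions: about 40% (Section 13.5), so 0.40 × 12 = 4.8, taken as 5; 0.40 × 24 = 9.6, taken as 10.
- Assumed, because the plan gives neither: the AUC that looks strong (0.80, with 0.85 and 0.90 shown) and the correlation between markers (0 to 0.7, equal for all pairs).

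**One unrelated marker.** With 5 remissions and 7 others, AUC = U/35, where U is the Mann-Whitney count. Allowing either direction, 84 of the 792 equally likely rank arrangements give 0.80 or more: 84/792 = 0.106. For 0.85 it is 38/792 = 0.048; for 0.90, 14/792 = 0.0177. With 10 and 14, the chance of 0.80 or more is 25,404/1,961,256 = 0.01295.

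**Best of 29 independent markers**, by 1 − (1 − p)^29:
- 12 patients, 0.80: 1 − 0.894^29 = 0.96
- 12 patients, 0.85: 1 − 0.952^29 = 0.76
- 12 patients, 0.90: 1 − 0.9823^29 = 0.40
- 24 patients, 0.80: 1 − 0.98705^29 = 0.31

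**Correlated markers.** Normal markers with equal correlation, remission count fixed, 20,000 simulated trials per setting; the correlation-0 column is the exact result above.

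| Fit | Values tested | AUC cut | Corr. 0 | Corr. 0.5 | Corr. 0.7 |
|---|---|---|---|---|---|
| 12 patients, 5 CR | 29 | 0.80 | 96% | 81% | 63% |
| 12 patients, 5 CR | 29 | 0.85 | 76% | 53% | 38% |
| 12 patients, 5 CR | 29 | 0.90 | 40% | 27% | 19% |
| 24 patients, 10 CR | 29 | 0.80 | 31% | 20% | 14% |
| 24 patients, 10 CR | 29 | 0.85 | 9% | 6% | 4% |
| 24 patients, 10 CR | 29 | 0.90 | about 1% | about 1% | about 1% |
| 12 patients, 5 CR | 58 | 0.80 | over 99% | 93% | 75% |
| 24 patients, 10 CR | 58 | 0.80 | 53% | 30% | 20% |

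The median best AUC among 29 unrelated markers in 12 patients is 0.89 (correlation 0) or 0.86 (correlation 0.5); in 24 patients it is 0.77 or 0.74. In fresh patients the chosen marker has a mean AUC of 0.50.

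These figures do not model a regimen effect. Some of the 29 antigens only define lineages, which lowers the effective count; subset-by-marker combinations raise it.

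**The case against.** The best counter-argument is that the plan never claims more than a descriptive screen. It declares no marker, sets no cut-off and selects no patient on these results. That stands, and it is why the point is minor. It does not remove the need for a chance reference, because a screen is useful only if its ranking can be told from noise. The hypothesis-generating caveat in Section 2.4.5.1 is about the T-cell repertoire work, not this analysis.

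A reader might infer that the plan will find a strong-looking marker in most trials whatever the truth. The documents do not support that as a general statement:
- The by-regimen sentence governs summaries; nothing says the logistic models are fitted by regimen. Pooled, 29 single markers reach 0.80 in a minority of null trials.
- The plan has no AUC cut. At 0.90, even the 12-patient fit falls below half.
- Fitting in-sample is itself inferred from the absence of any validation step.

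A reader might also argue from multi-marker models that separate 12 patients perfectly, or from a remission rate as high as the 5 of 6 seen at level A1 (Section 5.2.1). The plan fixes no model size, and its planning rate is about 40%, so I rest nothing on either.

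A formal gate is open to fair criticism too. At a 10% family-wise level in 24 pooled patients, a marker with true AUC 0.80 would pass in only about 36% to 49% of trials. Leave-one-out AUC is no remedy: pooled over such small samples it is biased low, averaging about 0.25 (12 patients) and 0.28 (24 patients) for a marker whose true AUC is 0.50.

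**Conclusion.** The gap is real but small in consequence. As written, apparent AUCs from at least 29 markers in two compartments would be reported with nothing to show what chance alone produces. How much this matters turns on a choice the plan leaves open. Fitted within a 12-patient regimen, noise alone often yields an impressive best AUC; pooled over 24 patients, it does so much less often. The sizes rest on 5 of 12 or 10 of 24 remissions, on the assumed AUC cuts and on equal correlation between markers. Primary safety, MTD and response conclusions do not depend on this analysis. It is worth correcting because the candidates are intended to feed later patient selection and the correction costs almost nothing.

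**What to change.** In Section 13.8.1 and Appendix C item 6:

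1. State that single-marker logistic models use both regimens pooled, with regimen as a covariate, and that per-regimen results are shown descriptively.
2. Report how many marker-by-compartment values were tested.
3. Show each AUC beside the permutation distribution of the maximum AUC over all values tested. Permute remission status within regimen, and recompute the same AUC statistic in every permutation. Use this as a reference, with no pass/fail gate.
4. Report any multi-marker signature only with a permutation reference that repeats the whole selection and fitting procedure, or with an optimism-corrected AUC. Do not use the pooled leave-one-out AUC.

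Cost: a few sentences and a short script; no new patients, samples or assays. The downside is that the reported AUCs will look less impressive beside their chance reference. The wording should be settled before marker data are analysed against outcome.
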